#### 5.5.4.1 CNR Calculated Based on Cerebrospinal Fluid

As described in the Section 4, CNR calculated based on cerebrospinal fluid (CNRCSF) is added as secondary criterion. CNRCSF will be analyzed as the primary criterion but limited to the following analyses: PPS analysis, FAS analysis, descriptive analysis overall and dose response.

CONFIDENTIAL	FORM STATISTICAL ANALYSIS PLAN N° GDX-44-004 VERSION 1.0	████████ Page 35 / 60
--------------	--	--------------------------

The tables and figures that will be displayed are detailed in Section 6.1.2.2.1 and the listings in Section 6.2.6.1.

#### 5.5.4.2 *Lesion-to-Brain Ratio*

As described in the Section 4, Lesion-to-Brain Ratio (LBR) is added as secondary criterion. LBR will be analyzed as the primary criterion but limited to the following analyses: PPS analysis, FAS analysis, descriptive analysis overall and dose response.

The tables and figures that will be displayed are detailed in Section 6.1.2.2.2 and the listings in Section 6.2.6.1.

#### 5.5.4.3 *Contrast Enhancement Percentage*

As described in the Section 4, Contrast Enhancement Percentage is added as secondary criterion. It will be analyzed as the primary criterion without adding the pre contrast administration value in the models but limited to the following analyses: PPS analysis, FAS analysis, descriptive analysis overall and dose response.

The tables and figures that will be displayed are detailed in Section 6.1.2.2.3 and the listings in Section 6.2.6.1.

#### 5.5.4.4 *Technical Adequacy of Images*

The adequacy of images was assessed by off-site readers and on-site radiologists as adequate or not and reason for inadequacy (with specification in case of other reason) recorded using a 5-items list.

Descriptive statistics for these secondary efficacy criteria will be presented by contrast agent group.

The tables and listings that will be displayed are detailed in Sections 6.1.2.2.4 and 6.2.6.2 respectively.

#### 5.5.4.5 *Lesion Detection Capacity*

The *number of enhancing lesions*, the *size of the three largest representative lesions through their largest diameter* and the *location of the three largest representative lesions* by subject were assessed by off-site readers and on-site radiologists for each dose of P03277 by contrast agent.

Descriptive statistics will be presented for the largest diameter (mm) and the location of each of the three most representative lesions according to the contrast agent group and for each of the three independent off-site readers and the on-site reader.

The number of enhancing lesions and the *largest diameter of the smallest lesion detected* will be analyzed in the same way with the following specifications:

- The exact number of enhancing lesions is not collected for off-site readings in case of > 10 lesions. A conventional value of 11 will be considered for both quantitative description and modeling (see below).
- The number of enhancing lesions will be described by presence of brain metastasis or not. This disposition is justified by an expected link of this stratification factor to the number of enhancing lesions.
- If  $\leq 3$  lesions are detected, the smallest lesion is the one with the smallest largest diameter. If  $> 3$  lesions are detected, the largest diameter of the smallest lesion is specifically collected.

CONFIDENTIAL	FORM	
STATISTICAL ANALYSIS PLAN N° GDX-44-004		Page 36 / 60
VERSION 1.0      DATED: 09JAN2018		

The number of enhancing lesions will be fitted by a multivariate model also. The negative binomial distribution is more appropriate than the more standard Poisson one for modeling lesion count data (see [5] in multiple sclerosis) and will therefore be used.

The dependent variable will be the count of enhancing lesions. The model will include the factor contrast agent group and period. The model will be limited to the subjects with presence of brain metastasis which is supposed to be linked to the number of enhancing lesions. Each off-site reader will be analyzed by a specific model and on-site reading will be analyzed in the same way. The parameters of the model will be estimated using the SAS® procedure Glimmix. The difference between contrast agent groups in mean of lesions detected and associated 95% CI will be computed for each dose of P03277.

For each dose of P03277 SAS® procedure used for the analyses of this secondary efficacy criterion will be the following for each off-site reader and on-site reading:

```

proc glimmix data = XXX;
  class subject trt period;
  model eval = trt period / dist = negbin link = id;
  random _residual_ / subject = subject type = cs;
  lsmeans trt / pdiff = controlu('MultiHance') tdiff cl alpha = 0.025;
  lsmeans trt;
  estimate "P03277 - MultiHance" trt 1 -1 /cl;
run;

```

The number of lesions detected on off-site readings will be listed only.

The *absence of contrast enhancement* is defined **at lesion level** by a degree of contrast enhancement equal to 1 = no: no enhancement. The absence of contrast enhancement will be analyzed **at subject level** only by considering its absence as soon as it is absent for all lesions. It will be presented by descriptive statistics.

The tables and listings that will be displayed are detailed in Sections 0 and 6.2.6.2 respectively.

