### 7.2.2 *Lesion detection capacity (on-site and off-site reads)*

Number, size and location of lesions detected and the presence or absence of enhancement will be recorded.

For each combined image set (1a, 2) and (1b, 3), the investigator/independent blinded reader is to record the following:

- Number of lesions
- For the 3 most representative lesions, the following will be recorded for each lesion separately:
  - The largest diameter of the lesion
  - The location of the lesion

- Presence or absence of enhancement (based on the evaluation ‘Degree of contrast enhancement (see [7.2.3](#)))
- In case that more than 3 lesions are present, the investigator/independent blinded reader has to enter in the eCRF how many lesions are present (total number) and to specify the diameter of the smallest lesion.

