### ***7.2.3 Lesion visualization variables (on-site and off-site reads)***

The investigator/ independent blinded reader will record each of lesion visualization variables (lesion border delineation, internal morphology and degree of contrast enhancement) for up to 3 most representative enhancing lesions, referring mainly to axial 3D T1-weighted GRE images for brain and sagittal T1-weighted SE/TSE images for spine, on a 4-point scale of the combined images sets (1a, 2) and (1b and 3).

- Border delineation:

Delineation of the lesion border is defined as the distinction of lesion from surrounding tissues, structures, or edema; and the detection of extent of the lesion (for extra-axial lesions, this pertains to the definition of the space in which the lesion is present, and for intra-axial lesions, it pertains to the invasion of white matter, gray matter, or both; the neuroanatomical distribution of the lesion; and its mass effect). This criterion will be assessed through the following scale:

- 1 = none: no or unclear delineation
- 2 = moderate: some areas of clear delineation but also with some significant areas of non-distinct delineation
- 3 = good: almost clear but not complete delineation
- 4 = Excellent: border outline is sharp with clear and complete delineation

- Internal morphology:

Internal morphology of the lesion includes an identification of lesion architecture and the intra-lesion features such as necrosis, hemorrhage and vascularity. This criterion will be assessed through the following scale:

- 1 = poor: poorly seen
- 2 = moderate: majority of lesion is poorly seen but with minor parts of lesion visible
- 3 = good: majority of lesion is clearly seen but with minor parts of lesion invisible
- 4 = excellent: lesion is well seen and can see “through” lesion to observe any complex areas of necrosis or hemorrhage or cyst formation.

- Degree of contrast enhancement:

This criterion will be a qualitative assessment according to the following scale:

- 1 = no: no enhancement
- 2 = moderate: weakly enhanced
- 3 = good: clearly enhanced
- 4 = excellent: clearly and brightly enhanced

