- The localization of the three largest representative lesions by subject will be assessed by off-site readers and on-site radiologists for each dose of P03277 by treatment groups. Localization of lesion will be displayed for each dose of P03277 by treatment groups; off-site and on-site reader's outcomes will be separately analyzed.

- The presence or absence of contrast enhancement for the three largest representative lesions will be assessed by off-site readers and on-site radiologists for each dose of P03277 by treatment groups. Contrast enhancement of lesion will be displayed for each dose of P03277 by treatment groups; each off-site and on-site reader's outcomes will be separately analyzed.

- **Diagnostic confidence**

- The diagnosis of each lesion according to off-site readers and on-site radiologists when evaluating each dose of P03277 by treatment groups will be displayed; off-site and on-site reader's outcomes will be separately analyzed.

- The level of diagnostic confidence of off-site readers and on-site radiologists when evaluating each dose of P03277 by treatment groups will be graded using a 5-point scale with the following points: nil, poor, moderate, high and excellent. Diagnostic confidence will be tabulated for each dose of P03277 by treatment groups; off-site and on-site reader's outcomes will be separately analyzed.

- **Overall diagnostic preference**

- The level of overall diagnostic preference of images of off-site readers when evaluating in global matched-pairs fashion all post contrast T1-weighted images (i.e. axial 3D T1

weighted GRE for brain and sagittal T1-weighted SE/TSE for spine of blinded images MRI 1 versus MR2) for each dose of P03277 will be evaluated according to their preference: for the overall diagnostic, MRI 1 is preferred to MRI 2, no difference between the 2 MRIs or MRI 2 is preferred to MRI 1.

For the analysis, the results will be displayed as follows:

- P03277 is preferred to MultiHance®
- No difference between the 2 treatments
- MultiHance® is preferred to P03277

Diagnostic preference of images will be tabulated for each dose of P03277.

- The reason of this preference will be displayed.
- **Impact of contrast agent-enhanced MRI on subject treatment plan:**
  - The impact on subject treatment plan will be assessed by on-site radiologists and will be summarized for each dose of P03277 by treatment groups.

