#### RATIONALE FOR ANY DEVIATION FROM PRE-SPECIFIED ANALYSIS PLAN PERFORMED

It was planned in the protocol to repeat on the PPS the evaluation of secondary efficacy criteria in case of a difference from the FAS by more than 15%. It has been decided that only the analyses of data from off-site readings for some relevant secondary criteria will be repeated on the PPS.

Further, three secondary criteria have been added since the last amendment: The Contrast-to-Noise Ratio calculated based on the noise issued from the CerebroSpinal Fluid (CSF): CNRCSF, the Lesion-to-Brain Ratio (LBR) and the Contrast enhancement percentage. The three criteria are calculated by subject, and by independent blinded reader in a centralized procedure (off-site readers) and the result is provided by exam for each reader by averaging the parameter for maximum 3 enhanced lesions.

$\text{CNR}_{\text{CSF}}$  is derived for each lesion, from the SI measurement, according to the following formula:

$$\text{CNR}_{\text{csf}} = \frac{SI_{\text{lesion}} - SI_{\text{ht}}}{SD_{\text{noise}}}$$

where  $SJ_{lesion}$  = the SJ in the ROJ in the lesion.

$SI_{bt}$  = the SI in the ROI in the lesion.

SDnoise ≡ SD of CSF noise

LBR is derived for each lesion, from the SI measurement, according to the following formula:

$$\text{LBR} = \frac{SIlesion}{SIht}$$

where  $SJ_{lesion}$  = the SJ in the ROI in the lesion.

$SI_{ht}$  = the SI in the ROI in the lesion.

Contrast enhancement percentage is derived for each lesion, from the SI measurement, according to the following formula:

$$\text{Contrast Enhancement Percentage} = \frac{SI_{post} - SI_{pre}}{SI_{pre}}$$

where  $SI_{post}$  = the SI in the ROI in the lesion post contrast media administration.  
 $SI_{pre}$  = the SI in the ROI in the lesion pre contrast media administration.

These three criteria will be analyzed as the primary criterion.

CONFIDENTIAL	FORM	
STATISTICAL ANALYSIS PLAN N° GDX-44-004		Page 18 / 60
VERSION 1.0      DATED: 09JAN2018		

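### The SAP counts contrast enhancement as absent only when every lesion in a subject fails to enhance, so this summary masks partial non-enhancement that the protocol planned to show by lesion; the change is not declared.

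*SAP*

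**What the plan says.** Protocol 7.2.2 sets the collection unit: "For the 3 most representative lesions, the following will be recorded for each lesion separately". Presence or absence of enhancement is one of the items, derived from the degree-of-enhancement grade in 7.2.3. Protocol 12.3 then sets the analysis: "The presence or absence of contrast enhancement for the three largest representative lesions will be assessed by off-site readers and on-site radiologists", and "Contrast enhancement of lesion will be displayed for each dose of P03277 by treatment groups", with each reader's results analysed separately.

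SAP 2.2.2 keeps the criterion for the three most representative lesions: grade 1 is absent, grades 2 to 4 are present. SAP 5.5.4.5 defines absence for a lesion "by a degree of contrast enhancement equal to 1 = no: no enhancement", but restricts the analysis to subject level, "only by considering its absence as soon as it is absent for all lesions". On presentation it says: "It will be presented by descriptive statistics".

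In the same SAP section, lesion diameter and location keep a display for each of the three lesions. Of the items that 7.2.2 records per lesion, only enhancement is collapsed to subject level.

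SAP section 4 declares two changes from the protocol's analysis: that "only the analyses of data from off-site readings for some relevant secondary criteria will be repeated on the PPS", and that three signal-intensity criteria are added. It does not mention the enhancement summary.

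**The concern.** The rule has two outcomes for a subject: all lesions non-enhancing, or everything else. The second mixes subjects whose lesions all enhance with subjects in whom one or two of three do not. A low dose that leaves some lesions unenhanced could look the same in this table as a dose that enhances all of them.

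This matters more than usual for a descriptive secondary criterion, for two reasons. First, the primary CNR is averaged over enhanced lesions matched on both examinations, so a lesion that does not enhance on one of them tends to leave the primary endpoint and does not count against the dose. Second, SAP 5.5.1.5 bases the choice of dose on primary and secondary efficacy criteria together, and allows a dose not shown superior on CNR to be recommended. The secondary summaries can therefore carry weight in the decision.

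**Working it through.** The documents give no figure for this criterion, so there is none to reproduce. The check has three parts.

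**1. The texts side by side**

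| Step | Protocol | SAP |
|---|---|---|
| Unit recorded or defined | each of up to 3 lesions (7.2.2) | each lesion, grade 1 = absent (2.2.2, 5.5.4.5) |
| Unit summarised | lesion enhancement by dose, agent, reader (12.3) | subject only, absent if all lesions absent (5.5.4.5) |
| Declared as a change | – | not in section 4 |

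**2. How much the rule can hide (illustration)**

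Assume each of a subject's k lesions fails to enhance with probability q, independently. Both q and independence are assumptions. Then:

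- flagged by the SAP rule: P(all) = q^k
- at least one lesion non-enhancing: P(any) = 1 − (1 − q)^k
- partial and unflagged: P(any) − P(all)

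| q | k | Flagged | Any | Partial, unflagged |
|---|---|---|---|---|
| 5% | 2 | 0.25% | 9.75% | 9.5% |
| 5% | 3 | 0.0125% | 14.26% | 14.25% |
| 10% | 2 | 1% | 19% | 18% |
| 10% | 3 | 0.1% | 27.1% | 27.0% |
| 20% | 2 | 4% | 36% | 32% |
| 20% | 3 | 0.8% | 48.8% | 48.0% |
| 40% | 2 | 16% | 64% | 48% |
| 40% | 3 | 6.4% | 78.4% | 72.0% |

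For k = 1, flagged = any = q, so nothing is lost.

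On the planned 60 randomised subjects per dose (50 + 10, Protocol section 8), if all had three lesions and q were 20%, the rule would flag 60 × 0.008 = 0.5 subjects and leave 60 × 0.48 = 28.8 with partial non-enhancement unflagged.

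Positive correlation narrows the gap. Suppose that with probability r all of a subject's lesions share one outcome, and otherwise they are independent. Then flagged = r·q + (1 − r)·q^k, and partial is multiplied by (1 − r). With q = 20%, k = 3 and r = 0.5, flagged = 0.5 × 0.2 + 0.5 × 0.008 = 10.4%, and partial = 0.5 × 48% = 24%. At r = 1, flagged = 20% and partial = 0.

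**3. Whether other planned outputs fill the gap**

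- *Number of enhancing lesions.* It is described by agent and reader in subjects with and without brain metastasis, and modelled in those with metastasis. It would move: with three lesions the mean is 3(1 − q), so 2.85 at q = 5% and 2.40 at q = 20%. But lesions detected off-site are only listed, so the SAP text gives no tabulated proportion of lesions enhancing. Off-site counts above 10 are set to 11.
- *Degree-of-enhancement sum score.* It is described and modelled by dose and reader, but does not isolate grade 1. With three lesions, totals of 6, 7, 8 and 9 can arise with or without a non-enhancing lesion (1 + 3 + 3 = 2 + 2 + 3 = 7). With two lesions, the same holds for 4 and 5. A single lesion graded 4 scores 4; recording a second, non-enhancing lesion raises the total to 5.
- *Listings.* They hold the individual data but give no summary by dose.

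**The case against.** The strongest reply is that a reader might infer from the rule that partial non-enhancement cannot be seen at all. The documents do not support that. The enhancing-lesion count, the sum score and the listings all carry some of the information, and within-subject losses against MultiHance would show in the count. This stands. What remains is that these routes are indirect.

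A reader might also infer that the variable must be close to zero in every arm and so cannot separate doses. That would need a known lesion-level rate, near-independence and mostly multi-lesion subjects, and the documents give none of these. Lesions in one subject share dose, timing and scanner, so positive correlation is plausible. Inclusion requires only one expected enhancing lesion, and a lesion expected from earlier imaging need not enhance at a low study dose. A subject with no enhancing lesion is a complete failure and a legitimate thing to report. This stands too.

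A third inference is that grade 1 could hardly occur, because Protocol 7.2.3 asks for grades "for up to 3 most representative enhancing lesions". The wording does sit badly with 7.2.2. But the scale in 7.2.3 itself includes a grade for no enhancement, 7.2.2 takes presence or absence from that grade, and Protocol 12.3 and SAP 5.5.4.6 speak of representative lesions without limiting them to enhancing ones. If grade 1 really was unavailable, a per-lesion table would also be nearly empty. The SAP describes grading in the past tense, so rewording cannot change reads already recorded.

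Two further cautions are fair. Protocol 12.3 implies a lesion-level display without using that term. And the SAP's table list and shells are not in the public copy, so a per-lesion table there cannot be ruled out, although the restriction to subject level in 5.5.4.5 makes it unlikely.

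**Conclusion.** The point holds in limited form. SAP 5.5.4.5 replaces the protocol's per-lesion display with an all-lesions subject rule, and section 4 does not say so. In subjects with two or three lesions, partial non-enhancement is masked in this summary and visible only indirectly elsewhere.

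The size of the loss in this trial is unknown. The illustrated range for three lesions, about 0.01% to 6% flagged against 14% to 72% partial, rests on assumed rates of 5% to 40% and on independence. It marks what the rule can hide, not what it will hide. The criterion is secondary and descriptive, so no error rate, power or sample size changes. It deserves correction because secondary criteria may inform the choice of dose and because the remedy is cheap.

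**What to change.** - Add a per-lesion table of enhanced/not enhanced by dose, agent and reader, which restores what Protocol 12.3 planned.
- Beside the all-lesions proportion, give the number and percentage of subjects with none, some and all of their graded lesions non-enhancing. Show this by number of graded lesions, since one-lesion subjects cannot fall in the middle category.
- Record any remaining departure from the protocol in SAP section 4.
- When reporting, state whether grade 1 was recorded for any representative lesion or only among lesions already judged enhancing, because Protocol 7.2.2 and 7.2.3 can be read differently. Without this, a low count of non-enhancing lesions cannot be interpreted.

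Cost: one descriptive table from grades already collected, and a line in section 4. No new reads and no change to the primary analysis are needed.

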#### 5.5.4.6 *Lesion Visualization Variables*

Off-site blinded readers and on-site radiologists graded the lesion visualization of the three largest representative lesions, using 3 variables (*lesion border delineation, internal morphology and degree of contrast enhancement*) assessed on a 4-point scale ranging from 1 to 4. For each variable, one subject score will be computed in adding up all lesion scores within subject by contrast agent.

The above lesion variables will lead to 3 scores **at subject level** consisting in adding up scores of lesions for each subject: border delineation sum of scores, visualization of internal morphology sum of scores and degree of contrast enhancement sum of scores.

For each of the three lesion variables, a sum of scores will be computed. Endpoints are defined based on a 4-point scale ranging from 1 to 4 for the 3 most representative lesions.

The sum of scores for each of the three variables will be calculated as follows: Sum of scores = score of the lesion number 1 + score of the lesion number 2 + score of the lesion number 3. The sum of scores for each of

CONFIDENTIAL	FORM	
STATISTICAL ANALYSIS PLAN N° GDX-44-004		Page 37 / 60
VERSION 1.0      DATED: 09JAN2018		

the lesion endpoints will range from 0 to 12. The following rules will apply independently for each of the three variables:

- In case of absence of lesions, the sum of scores will be equal to 0.
- In case of one or two lesions only, the collected score(s) will be considered and added in case of two.
- If one score is missing for one lesion then the sum of scores will be missing.

For each dose of P03277, the two contrast agent groups will be compared using a mixed model for correlated data. Each mixed model will be performed for the three independent off-site readers and the on-site reader.

For each mixed model, the dependent endpoints will be the sum of scores of lesion border delineation, the sum of scores of visualization of lesion internal morphology and the sum of scores of degree of lesion contrast enhancement, respectively.

The models will include the contrast agent group and the period. The parameters of the mixed models will be estimated using the SAS® procedure Mixed. The difference between contrast agent groups in mean score and associated 95% CI will be computed for each dose of P03277.

Analyses using the FAS will be restricted to subjects whose the criterion of interest (lesion border delineation, internal morphology or degree of contrast enhancement) is available at both MRIs.

For each dose of P03277 SAS® procedure used for the analyses of these secondary efficacy criteria will be:

```

proc mixed data = XXX method = REML;
  class subject trt period;
  model eval = trt period;
  random subject / type = cs;
  lsmeans trt / pdiff = controlu('MultiHance') tdiff cl alpha = 0.025;
  lsmeans trt;
  estimate "P03277 - MultiHance" trt 1 -1 /cl;
run;

```

Descriptive quantitative statistics for the 3 sums of scores for border delineation, visualization of internal morphology and degree of contrast enhancement will be presented by contrast agent group for each dose of P03277.

The tables and listings that will be displayed are detailed in Sections 0 and 6.2.6.2 respectively.

